11.5 OTHER SAFETY PARAMETERS

Other safety parameters include [REDACTED], C-SSRS, and EPS scales (AIMS, BARS, and SAS).

[REDACTED]

11.5.2 Columbia-Suicide Severity Rating Scale

For the C-SSRS, the number and percentage of patients with suicidal ideation or suicidal behavior, as recorded on the C-SSRS scale, will be presented overall for the OLTP and by treatment group for the DBTP. The distribution of response for most severe suicidal ideation and suicidal behavior during the lifetime history, the OLTP, and the DBTP will be presented overall for the OLTP and by treatment group for the DBTP. Supportive listings will be provided, including the PID number, treatment group (for DBTP only), visit number, lifetime history, and postbaseline values for each patient. Intensity of ideation, suicidal behavior type, and lethality of suicidal behavior will also be included in these listings. Listings of all AEs occurring in patients who have suicidal ideation or suicidal behavior during OLTP and DBTP will also be provided.

11.5.3 Extrapyramidal Symptom Scales

A patient will be considered to have treatment-emergent parkinsonism if the patient's SAS score was ≤ 3 at baseline and > 3 at any postbaseline assessment. A patient will be considered to have treatment-emergent akathisia if the patient's BARS score was ≤ 2 at baseline and > 2 at any postbaseline assessment. The number and percentage of patients with treatment-emergent parkinsonism or akathisia will be tabulated overall for the OLTP and by treatment group for the DBTP. Listings of patients with treatment-emergent parkinsonism or akathisia will be provided, including the PID number, baseline and postbaseline values. Listings of all AEs for patients with treatment-emergent parkinsonism or akathisia will also be provided.

Cariprazine
RGH-MD-25 – Statistical Analysis Plan
Amendment #3 – 23 November 2022

Descriptive statistics (n, mean, standard deviation, median, minimum and maximum) for the total scores and the changes from baseline values at every assessment timepoint for each EPS scale (AIMS, BARS, and SAS) will be presented overall for the OLTP and by treatment group for the DBTP.

12.0 HEALTH OUTCOMES ANALYSES**Work Productivity and Activity Impairment Questionnaire Bipolar Disorder
(WPAI-BD)**

The Health Outcome endpoint is change from baseline in percent work time missed, percent impairment while working, percent overall impairment, and percent activity impairment due to bipolar disorder at Week 16 for OLTP, and at Double-blind Weeks 8 and 39 for DBTP, as assessed by the WPAI-BD.

Descriptive statistics (n, mean, standard deviation, median, Q1, Q3, minimum and maximum) will be provided by visit for the OL ITT population and the DB ITT populations.

Baseline for this HEOR endpoint during the DB treatment period for the DB ITT population will be defined as the last nonmissing efficacy assessment before the first dose of DB IP.

The change from baseline will be analyzed during the DB treatment period for the DB ITT population, by using an MMRM with treatment group, region (US and non-US), modified index episode strata (manic or depressive), visit, and treatment group-by-visit interaction as fixed effects, and the baseline value and baseline-by-visit interaction as the covariates. An unstructured covariance matrix will be used. The analysis will be performed based on post-DB baseline using only the OC without imputation of missing values.

WPAI:BIPOLAR DISORDER Related Endpoints Derivation

WPAI outcomes are expressed as impairment percentages, with higher numbers indicating greater impairment and less productivity, i.e., worse outcomes, as follows:

Questions:

- Q1 = Currently employed (working for pay).
- Q2 = During past 7 days, missed work hours because of problems associated with your bipolar disorder
- Q3 = During past 7 days, missed work hours due to other reason, such as vacation, holidays, time off to participate in this study
- Q4 = During past 7 days, how many hours actually worked
- Q5 = During past 7 days, how much bipolar disorder affected productivity while working

- Q6 = During past 7 days, how much bipolar disorder affected regular daily activity.

Scores:

Multiply scores by 100 to express in percentages.

- Percent work time missed due to bipolar disorder (absenteeism): $Q2/(Q2 + Q4)$
- Percent impairment while working due to bipolar disorder (presenteeism): $Q5/10$
- Percent overall work impairment due to bipolar disorder (overall work productivity loss): $Q2/(Q2 + Q4) + (1 - (Q2/(Q2 + Q4))) \times (Q5/10)$
- Percent activity impairment due to bipolar disorder (regular activity impairment): $Q6/10$

If the response to Q1 (“Currently employed?”) is No or missing, absenteeism, presenteeism, and overall work productivity loss will all be set to missing.

13.0**INTERIM ANALYSIS**

No interim analysis is planned for this study.

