12.12 Work Productivity and Activity Impairment Questionnaire: Bipolar Disorder (WPAI-BD)

[figure not shown]
The following questions ask about the effect of your bipolar disorder on your ability to work and perform regular activities. *Please fill in the blanks or circle a number, as indicated.*

Are you currently employed (working for pay)? ____NO __YES If NO, check "NO" and skip to question 6.
 The next questions are about the past seven days, not including today.
 During the past seven days, how many hours did you miss from work because of problems associated with your bipolar disorder? Include hours you missed on sick days, times you went in late, left early, etc. because of bipolar disorder. Do not include time you missed to participate in this study. ____HOURS
 During the past seven days, how many hours did you miss from work because of any other reason, such as vacation, holidays, time off to participate in this study? ____HOURS
 During the past seven days, how many hours did you actually work? HOURS (If "0", skip to question 6)

5) During the past seven days, how much did bipolar disorder affect your productivity while you were working? Think about days you were limited in the amount or kind of work you could do, days you accomplished less than you would like, or days you could not do your work as carefully as usual. If bipolar disorder affected your work only a little, choose a low number. Choose a high number if bipolar disorder affected your work a great deal.

6) During the past seven days, how much did bipolar disorder affect your ability to do your regular daily activities, other than work at a job? By regular activities, we mean the usual activities you do, such as work around the house, shopping, child care, exercising, studying, etc. Think about times you were limited in the amount or kind of activities you could do and times you accomplished less than you would like. If bipolar disorder affected your activities only a little, choose a low number. Choose a high number if bipolar disorder affected your activities a great deal.

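### The SAP gives no rule for WPAI-BD overall work impairment when an employed patient worked zero hours and missed some because of bipolar disorder; coded literally, a known 100% becomes missing

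*SAP*

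**What the plan says.** The WPAI-BD form in Protocol Attachment 12.12 routes patients by hours worked. Its fourth question reads "During the past seven days, how many hours did you actually work? HOURS (If '0', skip to question 6". A patient who worked no hours therefore never sees Q5, the rating of how far bipolar disorder affected productivity at work.

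SAP 12.0 derives four scores, each multiplied by 100:

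- Absenteeism: Q2/(Q2 + Q4).
- Presenteeism: Q5/10.
- Overall work impairment, labelled "Percent overall work impairment due to bipolar disorder (overall work productivity loss": absenteeism plus (1 − absenteeism) × Q5/10.
- Activity impairment: Q6/10.

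Higher values are worse. The section has one missing-score rule: if Q1 (employment) is No or missing, "absenteeism, presenteeism, and overall work productivity loss will all be set to missing". On the MMRM it says: "The analysis will be performed based on post-DB baseline using only the OC without imputation of missing values".

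No other section fills the gap. SAP 16.2 gives missing-item rules for MADRS, YMRS, AIMS, SAS and BARS, but none for WPAI-BD. Protocol 7.3.6 deferred the health-economics analysis to a separate plan. The amendment summary in SAP Appendix IV records that this arrangement was dropped and that the material now belongs in this SAP.

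**The concern.** The form and the formula do not fit together for one type of patient: employed, no hours worked in the past week, and some hours missed because of bipolar disorder. The formula asks for an item that the form tells this patient not to answer, yet the answer is not needed because the item carries zero weight.

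If the score is lost, the loss depends on the outcome. It removes values at the top of the scale and nothing else, and neither the observed-case summaries nor the MMRM restores them. The setting makes such patients plausible. WPAI-BD is given at Screening, during an acute episode and when a hospital stay is permitted. It is given again at Visit 31/ET, which patients who relapse undergo.

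**Working it through.** **Inputs.** The skip at Q4 = 0 comes from Protocol Attachment 12.12. The formulas and the single missing-score rule come from SAP 12.0. The software is SAS 9.4 or newer (SAP 15.0), in which + and × return missing if any operand is missing, including 0 × missing. The plan states no figure on this point to reproduce.

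**Step 1: the value when Q4 = 0 and Q2 > 0.** Write A for absenteeism.

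A = Q2/(Q2 + 0) = 1

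Overall = A + (1 − A) × Q5/10 = 1 + 0 × Q5/10 = 1

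Evaluated for each Q5 from 0 to 10, the result is 100% every time. The value is therefore known without Q5.

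**Step 2: the formula as written, over response patterns.** Q5 is missing whenever Q4 = 0.

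| Q2 | Q4 | Q5 | Absenteeism | Overall, coded literally | Overall, with the rule under fix |
|---|---|---|---|---|---|
| 0 | 40 | 0 | 0% | 0% | 0% |
| 20 | 20 | 5 | 50% | 50% + 50% × 0.5 = 75% | 75% |
| 36 | 4 | 10 | 90% | 90% + 10% × 1.0 = 100% | 100% |
| 39 | 1 | 8 | 97.5% | 97.5% + 2.5% × 0.8 = 99.5% | 99.5% |
| 40 | 0 | skipped | 100% | missing | 100% |
| 8 | 0 | skipped | 100% | missing | 100% |
| 0 | 0 | skipped | 0/0 | missing | missing |

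A patient who missed 39 hours and worked one scores 99.5% and is kept. A patient who missed 40 and worked none is dropped. Scores with Q4 > 0 are the same in both columns.

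**Step 3: effect on the mean at one visit.** Let s be the share of employed patients with Q4 = 0 and Q2 > 0, and m the mean overall score of the others. The literal mean is m. The correct mean is s × 100% + (1 − s) × m. The understatement is s × (100% − m). The documents give neither s nor m, so the values below are assumptions.

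| s | m = 20% | m = 40% |
|---|---|---|
| 2% | 0.02 × 80 = 1.6 points | 0.02 × 60 = 1.2 points |
| 5% | 0.05 × 80 = 4.0 points | 0.05 × 60 = 3.0 points |
| 10% | 0.10 × 80 = 8.0 points | 0.10 × 60 = 6.0 points |

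**Step 4: change from baseline.** The planned endpoint is a change, so Step 3 does not carry over directly. Losing a 100% at baseline removes a patient who could only stay level or improve. Losing a 100% at a later visit removes a patient who could only stay level or worsen. The two push the mean change in opposite directions, so its net bias cannot be signed from the documents.

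**The case against.** **The SAP does not say that the score becomes missing.** This is correct. The loss follows from coding the formula with ordinary arithmetic operators. A programmer who used the SAS SUM function, which ignores missing terms, would get 100%, and the SAP supplies no WPAI-BD code. What stands is that the handling is unspecified, that the stated formula followed literally loses the value, and that the result depends on an undocumented programming choice.

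**A reader might infer that every employed patient with zero hours is wrongly lost, and that these are the most impaired patients.** The documents do not support that. With Q2 = 0 and Q4 = 0, for example a week of vacation entered under Q3, the ratio is 0/0 and missing is the proper result. Q3 is also outside the formula, so a patient with 8 hours missed for bipolar disorder and the rest of the week on holiday scores 100% too. The lost values are the worst on the score, but the patients need not be the most ill.

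**A reader might also infer that the contrast between arms is biased towards no difference, because placebo patients relapse more.** SAP 14.0 assumes 35% relapse on placebo and a hazard ratio of 0.42, which implies about 1 − 0.65^0.42 = 17% on active treatment. That shows an expected difference in relapse. It does not show a difference in full absence from work among employed patients at the analysed visits. Relapsing patients are discontinued (Protocol 8.9), so their next WPAI-BD is at Visit 31/ET. Whether that visit maps to double-blind Week 8 or Week 39 depends on SAP Table 16.1-8, which the public copy does not show. The share employed, and the share fully absent by arm, are not given.

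**The stakes are small.** This stands. Protocol 6.5 describes the health-economics analyses as exploratory, there are no secondary endpoints, and WPAI-BD is outside the sequential test. Absenteeism (100%) and activity impairment are still computed for these patients, so full absence remains visible in the results. Presenteeism is properly undefined for someone who did not work.

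**Conclusion.** The point holds for employed patients with Q4 = 0 and Q2 > 0, and for the overall work impairment score only. It goes beyond missing detail, because the formula followed as written discards values that are known to be 100% while keeping near neighbours such as 99.5%.

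The mean at a visit is understated whenever such patients exist and the others average below 100%. The range of about 1.2 to 8.0 points rests wholly on the assumed shares and means, and on literal coding. Bias in the arm contrast, and its direction, is not demonstrated. No primary or safety conclusion is affected.

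**What to change.** Add to the derivation rules in SAP 12.0:

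- If Q1 = Yes, Q4 = 0 and Q2 > 0, overall work impairment is 100% and presenteeism is missing.
- If Q2 + Q4 = 0, absenteeism, presenteeism and overall work impairment are missing.

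The first rule restores a value already fixed by the answers given. The second records what the formula implies and prevents a division by zero. The cost is two sentences in the SAP and two lines in the derivation program. No new data are needed.

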14.0 DETERMINATION OF SAMPLE SIZE

The sample size and power calculations are based on the analysis of time to relapse of any mood episode in the DBTP to compare each cariprazine dose group versus placebo-based on a log-rank test. The trial will be a fixed follow-up design. Patients are followed from randomization until dropout, relapse or a fixed duration of 39 weeks.

The relapse HR is assumed to be 0.42 based on cariprazine maintenance study in patients with schizophrenia ([Durgam 2016](#)) [REDACTED] compounds (asenapine and aripiprazole) in bipolar I disorder trials and schizophrenia maintenance trials were similar ([Pigott 2003; Keck 2006; Kane 2011; Szegedi 2018](#)). The cumulative relapse rate at Week 39 for the placebo group is assumed to be 35%, which is the average of the relapse rate in the placebo arm at Week 39 for the asenapine bipolar mania maintenance trial ([Kane 2011](#)) and the quetiapine bipolar I disorder maintenance trial ([Suppes 2009](#)).

Using these assumptions, the study would have to observe approximately 75 events to have 85% statistical power to detect that at least 1 dose is significant. The statistical method for the power calculation is based on the log-rank 2-sided test at the 5% significance level to compare the difference of each of the 2 survival curves of the cariprazine treatment groups versus that of placebo. Based on the assumed event rates, and considering the 26% of patients who may discontinue early from the study due to other reasons, approximately a total of 378 patients should be randomized to cariprazine 3.0 mg/d, cariprazine 1.5 mg/d, and placebo, or approximately 126 patients per treatment group.

It should be noted that this study is designed to test the 3.0 mg/d dose of cariprazine versus placebo first at the 0.05 significance level and, if the results are significant, then the 1.5 mg/d dose of cariprazine will be tested at the 0.05 significance level. Given this sequential testing strategy, the higher dose of 3.0 mg/d has 85% statistical power to show significance versus placebo, and the 1.5 mg/d dose, if it is as effective as the 3.0 mg/d dose, and the 3.0 mg/d dose is statistically significant, would also have 85% statistical power at the 0.05 significance level.

With the expectation that approximately 46% of patients will complete the OLTP period and will meet the randomization criteria, approximately 882 patients would be expected to enter and be treated with cariprazine in the OLTP.

Cariprazine
RGH-MD-25 – Statistical Analysis Plan
Amendment #3 – 23 November 2022

[figure not shown]
With the expectation of a 34% screening failure rate, approximately 1245 patients are expected to be screened. In the event that screening and/or randomization failure rates are higher than projected, enrollment will continue until approximately 126 patients per treatment arm are randomized. At the time the randomization target has been met, patients who have been screened, but are not yet randomized will be allowed to continue in the study until they complete the study, prematurely discontinue, or otherwise fail to meet randomization criteria.

15.0 STATISTICAL SOFTWARE

Statistical analyses will be performed using version 9.4 (or newer) of SAS on a Linux operating system.

[figure not shown]
16.0

DATA HANDLING CONVENTIONS

[figure not shown]

Cariprazine
RGH-MD-25 – Statistical Analysis Plan
Amendment #3 – 23 November 2022

[figure not shown]

Cariprazine
RGH-MD-25 – Statistical Analysis Plan
Amendment #3 – 23 November 2022

[figure not shown]

Cariprazine
RGH-MD-25 – Statistical Analysis Plan
Amendment #3 – 23 November 2022

[figure not shown]

[figure not shown]
Cariprazine
RGH-MD-25 – Statistical Analysis Plan
Amendment #3 – 23 November 2022

Cariprazine
RGH-MD-25 – Statistical Analysis Plan
Amendment #3 – 23 November 2022

16.2 DERIVED EFFICACY VARIABLES AND SAFETY VARIABLES

If only a few item scores are missing, the total score will be calculated based on available item scores using the following formula: (total number of items in the scale) \times (sum of nonmissing items / number of items with nonmissing values). The maximum number of missing items allowed for the total scores imputation is specified below.

- MADRS total score is the sum of the 10 items from the MADRS. If more than 2 items of the MADRS are missing, then the total score will be set to missing
- YMRS total score is the sum of the 11 items of the YMRS. If more than 1 item of the YMRS are missing, then the total score will be set to missing
- AIMS total score is the sum of the first 7 items of the AIMS. Possible range is 0 to 28, with each item ranging from 0 to 4. If more than 1 item of the first 7 AIMS items is missing, then the total score will be set to missing. Items 8 through 12 will be summarized separately (items 8-10 also range from 0-4 each, while items 11-12 are yes/no).
- SAS total score is the sum of the 10 items of the SAS. Possible range is 0 to 40, with each item ranging from 0 to 4. If more than 1 item for the SAS are missing, then the total score will be set to missing.
- BARS total score is the sum of the first 3 items (Q1, Q2a and Q2b) of the BARS. Possible range is 0 to 9, with each item ranging from 0 to 3. If any of these 3 BARS items is missing, then the total score will be set to missing. Q3 will be summarized separately as a single value score with possible range 0 to 5.

For the LOCF analysis, if a patient misses a postbaseline visit or if the postbaseline visit occurs outside the visit time window, a record for the scheduled visit will be imputed using the last nonmissing value immediately before the missing value. If the missing value occurs at Week 1, the baseline value will be carried forward for Week 1, provided that at least 1 subsequent postbaseline assessment is available. For a composite scale such as MADRS total score, individual items of a rating scale will not be carried forward. Only total scores will be carried forward using the last-observation-carried-forward approach.

Several ophthalmologic examinations were performed later than the visit dates of OLTP, hence the data will be reported by the examination dates within in the derived visit windows in the DBTP. Similarly, for the examination dates performed after the visit dates of DBTP, data will be reported in the SFU period according to the derived visit windows.

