- ^f C-SSRS may be assessed remotely, if needed, by a certified rater. Clinicians with a valid C-SSRS certification for another Allergan study may rate C-SSRS in the event the study-certified rater is unavailable to complete the assessment.
- g If visit is being performed remotely, study staff should verbally administer the WPAI-BD questionnaire to the patient and record the patient's responses in the source.
- Movement scales may be conducted remotely if needed. Where possible, telemedicine virtual visits or video calls (without recording) should be used to conduct this assessment remotely. If a scale item cannot be assessed, the item may be skipped and the source should indicate the item could not be assessed. Movement scales may only be conducted by raters certified on the scale. In the event a rater is not available, these assessments may be omitted and assessed at the next scheduled timepoint, or earlier, at an Unscheduled Visit.
- Blood pressure and pulse rate will be measured both standing and supine. If visit is being performed remotely, this assessment may be omitted at this timepoint; however, vital signs, including weight, should be obtained at the next scheduled in-home (where possible) or in-person visit.

- If visit is being performed remotely, this assessment may be omitted. Every attempt should be made to have patient complete as an unscheduled assessment during the SFU period.
- If visit is being performed remotely, this assessment may be omitted at this timepoint. Patient should have this assessment performed as an Unscheduled assessment during the Safety Follow-up period. Clinical findings upon termination must be followed until the condition returns to prestudy status or can be explained as unrelated to investigational product. If necessary, an additional follow-up visit should be scheduled.

If visit is being performed remotely or at an alternate laboratory facility, this assessment may be omitted. In consideration of the processing time required, pharmacokinetic samples should not be collected during in-home visits.

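### The missing-item rule can discard incomplete BARS and SAS ratings that already exceed the akathisia or parkinsonism cut-off, most plausibly at telephone or video visits

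*SAP*

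**What the plan says.** SAP 16.2 sets the scoring rules.

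- **BARS total:** the sum of three items. "Possible range is 0 to 9, with each item ranging from 0 to 3". No missing item is tolerated: "If any of these 3 BARS items is missing, then the total score will be set to missing".
- **SAS total:** the sum of ten items. "Possible range is 0 to 40, with each item ranging from 0 to 4". One missing item is tolerated: "If more than 1 item for the SAS are missing, then the total score will be set to missing".
- **Proration**, where missing items are within the limit: "If only a few item scores are missing, the total score will be calculated based on available item scores using the following formula", namely the number of items times the mean of the rated items. It can apply to the SAS with one item missing, but never to the BARS.

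SAP 11.5.3 calls akathisia treatment-emergent if the "BARS score was ≤ 2 at baseline and > 2 at any postbaseline assessment". Parkinsonism is defined in the same way with an SAS cut-off of 3. The section neither provides for incomplete ratings nor states a denominator.

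Protocol 12.13.4 and the footnotes to Protocol Tables 4 and 5 allow the movement scales to be rated remotely under COVID-19 restrictions, with video preferred: "If a scale item cannot be assessed, the item may be skipped and the source should indicate the item could not be assessed".

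**The concern.** A limit on missing items is sensible for a continuous total, where an incomplete sum is biased low. For a yes/no criterion of the form total above a cut-off, it can throw away a result that is already settled. The protocol itself makes incomplete ratings foreseeable, since it permits remote rating of a scale that is largely a hands-on examination.

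At stake are the tabulated rates of treatment-emergent akathisia and parkinsonism, overall in the open-label period and by arm in the double-blind period. A patient whose only ratings above the cut-off were incomplete would not appear as a case. Because SAP 11.5.3 states no denominator, the same patient could be tabulated as a non-case.

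SAP 17.2 does not fill the gap. Its list of assessment categories missed because of COVID-19 does not name the movement scales.

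**Working it through.** **Plan's own figures.** BARS maximum: 3 items × 3 = 9. SAS maximum: 10 items × 4 = 40. Both match SAP 16.2. SAP 11.5.3 says only BARS score; I take this to be the three-item total, because SAP 16.2 summarizes the global item (Q3) separately.

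**Lower bound.** Every item scores 0 or more, so full total ≥ sum of rated items. A rated sum above the cut-off therefore proves that the full total is above it.

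**Which items can be rated remotely (Protocol 12.6 and 12.8).**

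- SAS items 3 to 7 (shoulder, elbow, wrist, leg, head) have the examiner move or hold the patient. Item 8 is a tap on the glabella. If these are skipped at a telephone or video visit, 5 or 6 items are missing against a limit of 1.
- By video, that leaves items 1, 2, 9 and 10 (gait, arm dropping, tremor, salivation). By telephone these too call for observation, so the SAS problem mainly concerns video.
- The BARS objective item is scored by watching the patient seated and standing. Video can serve; a telephone call cannot. The two subjective items can be asked by telephone.

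**BARS examples.**

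- Awareness 3, distress 3, objective item unrated: rated sum 6, true total between 6 and 9, cut-off > 2. Under SAP 16.2 the total is missing.
- Two items rated: 4 × 4 = 16 patterns. Sums of 0, 1 and 2 arise in 1 + 2 + 3 = 6 of them, so 16 − 6 = 10 already exceed 2. All 10 are set to missing.
- One item rated: 1 of 4 patterns (a score of 3) exceeds 2.
- Patterns with a rated sum > 2 but a full total ≤ 2: none, on full enumeration with one item left out.

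**SAS examples.**

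- Gait 2 and tremor 2, hands-on items skipped: the total is at least 4, cut-off > 3. Under SAP 16.2 it is missing.
- Items 1, 2, 9 and 10 rated: 5⁴ = 625 patterns. Sums of 0 to 3 arise in 1 + 4 + 10 + 20 = 35, so 625 − 35 = 590 already exceed 3. All are set to missing.

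These pattern counts show what is logically possible. They are not probabilities.

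**An inconsistency within the SAS rule.** Nine items rated with sum 3 prorate to 10 × 3/9 = 3.33, which counts as above 3, although the true total could be 3. Eight items rated with sum 12 mean a total of at least 12, yet the rating is missing. The rule can count an unproven case and drop a proven one.

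**Baseline.** The COVID-19 provisions apply only after Visit 2 is complete (Protocol 12.13), so they do not affect the baseline half of either definition.

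**The case against.** The strongest reply is that a prespecified limit on missing items is ordinary scoring practice, that these safety tables are descriptive, and that the signal survives elsewhere. EPS adverse events are tabulated by arm (SAP 11.1), BARS Q3 is summarized separately (SAP 16.2), rescue medication for EPS or akathisia is summarized (SAP 8.0), and all assessments are listed (SAP 16.3). The definitions also use any post-baseline assessment, and Protocol 6.6.7.1 schedules 16 post-baseline EPS visits. A patient is lost only if no visit has a valid total above the cut-off. All of this stands, and it is why the point is minor. It does not justify discarding a settled result.

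Stronger readings are tempting but unsupported:

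- **That every remote visit leaves SAS items unrated, so a remote SAS can yield no case.** Skipping is allowed, not required. Protocol 12.13.1 and 12.13.4.1 also permit home visits, where an examiner can rate every item. For telephone and video the gap is an inference from the item descriptions.
- **That the SAS total is lost whenever an item is missing.** With exactly one missing it is prorated, and the result can even over-count.
- **That the same problem reaches the relapse endpoint through the YMRS and MADRS.** The permission to skip items covers only the movement scales. Protocol 12.13.2 and SAP 17.1 require the YMRS and MADRS at remote visits, and relapse has other triggers.
- **That any repair is free of bias.** A denominator limited to patients with an evaluable rating would admit those with only partial ratings solely when positive. If two of ten such patients exceed the cut-off, they contribute 2/2 and the other eight vanish; a denominator independent of the score gives 2/10.

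**Conclusion.** The point holds in a limited form. SAP 16.2 and 11.5.3 together discard a BARS rating with any item missing, or an SAS rating with two or more missing, even when the rated items alone exceed the cut-off. Treatment-emergent akathisia and parkinsonism can be under-counted for patients with no other valid total above the cut-off.

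The size cannot be computed. The documents give neither the share of telephone or video visits nor the frequency of skipped items. The conclusion assumes that the BARS score in SAP 11.5.3 is the three-item total and that raters skip items they cannot perform as described. It concerns the EPS safety tables only; nothing here touches the primary endpoint.

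**What to change.** In SAP 16.2 and 11.5.3, for the SAS > 3 and BARS > 2 criteria only:

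1. Count the criterion as met at an assessment if the total under the present rule exceeds the cut-off, or if the sum of the rated items already does.
2. Leave the total missing, as now, for the continuous summaries.
3. State the denominator: patients with a baseline at or below the cut-off and at least one post-baseline assessment of the scale in the period, complete or partial.
4. Report separately, by period and arm, the number of patients whose only ratings were partial and below the cut-off.

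The cost is a few sentences in the SAP and simple programming. Step 1 cannot create a false case beyond what the present rule already allows. The small downside is that patients with only partial ratings below the cut-off count as non-cases, though some may truly exceed it; the count in step 4 makes that visible.
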